**7.10. Safety Evaluation**

Details about the safety reporting and adjudication for SYNSEQ can be found in the Safety Plan for the SYNSEQ study.

Adverse events and deaths will be summarized in tables with number of events, number and percentage of patients with one or more events, according to the characteristics given below.

**Adverse Events**

- Seriousness (investigator adjudication)
- Relatedness (AEAC adjudication)
  - Procedure

- System
- Unanticipated Serious Adverse Device Effect (USADE) (Medtronic adjudication)

Deaths (per AEAC adjudication)

- relatedness (system and/or procedure)
- cardiac classification
  - cardiac death
  - sudden cardiac death
  - non-sudden cardiac death
  - non-cardiac death
  - unknown

Another table will be reported with for each MedDRA preferred term the number of events, number of patients with one or more events, and percentage of patients with event.

The AEAC classification will be used for reporting if available. If the AEAC adjudication is not available, the investigator classification will be used. USADE adjudication is only performed by the sponsor Medtronic, and therefore the sponsor adjudication will be used here. If there is a disagreement between investigator and AEAC, this disagreement will be reported in forms of AE listing. Adverse events and device deficiencies will be summarized for the 'All Enrolled' cohort.

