- Multi-lead ECG (within last 3 months, otherwise a new ECG should be performed)
- Echocardiographic evaluation (if available within last 3 months, otherwise not collected)
- NYHA classification
- Medical history (cardiovascular or related)
- Cardiovascular medications

- Pregnancy test for women with child-bearing potential
- MRI as explained in paragraph below

F.2.1.1 Magnetic Resonance Imaging (MRI)

Patients will undergo a baseline MRI before scheduled CRT-related surgery (i.e. dedicated research study or EP procedure or actual CRT implant) to identify the location and transmural of any myocardial scar using late gadolinium enhancement-magnetic resonance imaging according to standard hospital practice. During the MRI a thorax scan is required to be able to reconstruct the thorax and lungs, i.e. a transverse scan with neck and liver visible. An appropriate marker should be placed on the xyphoid and 10 cm above the xyphoid during this scan. In addition, left ventricular end systolic volume (LVESV), left ventricular end diastolic volume (LVEDV) and left ventricular ejection fraction (LVEF) will be determined. MRI can be performed as standard of care or solely for the study. If the patient has a LBBB conduction pattern and QRS-width above 150ms, the MRI images should be analyzed before the EP study to detect the presence of scar. If no scar is present on late gadolinium enhancement MRI, the LBBB patient with QRS > 150ms should not be included in the study (if MRI done as standard of care) or should be exited from the study (if MRI done solely for the study).

F.2.2 Electrophysiological (EP) study visit

The EP study visit can be a standalone visit or can occur on the same day as the baseline visit. The EP study visit should take place within 3 months after the MRI has been obtained. Patients will undergo standard implant of a biventricular pacing system (CRT-P or CRT-D) or will undergo the EP study (data for this research study will be collected) before possible CRT-implant or will participate in this dedicated research study as a standalone visit (without any concomitant procedure).

If available in the center, a finger volume clamp system (e.g. model Nexfin, BMEYE B.V.) will be connected to one of the subject's fingers to measure the blood pressure non-invasively. In addition, a multi-lead surface ECG is collected during the whole procedure.

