## 7. Statistical Methods

### 7.1. Study Subjects

#### 7.1.1. Disposition of Subjects

A subject is enrolled in the study when he/she signs and dates the Patient Informed Consent. The study will enroll up to 40 subjects who fulfill the eligibility criteria and who have completed the EP study procedure. It is anticipated that this study will require approximately 12 to 18 months for subject enrollment. Patients' participation in this study is expected to last approximately between 1 day and 3 months, depending on the time between enrollment and the EP study and the duration of hospital stay after the research study, or EP related procedure, or the CRT-implant. Subjects will be exited from the study just before the moment of hospital discharge. There will be no further follow-up required for subjects that are exited from the study. A flow chart similar to Figure 1 will be created to describe patient disposition.

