### 7.1.3. Analysis Sets

This statistical analysis plan is created to support the final analysis of the SYNSEQ study. Study manager, scientists/engineers, data manager and statistician will determine the visit cut-off date and received data cut-off date for the final data base lock as suitable.

All patients who signed the informed consent document will be defined as the enrolled population. The Analysis Population is defined as patients who are enrolled, have no inclusion or exclusion criteria violation regarding the most important criteria, i.e., inclusion criteria 1 and 2 and exclusion criterion 3, and have less than 3 months between MRI and EP visit.

The EP study visit should take place within 3 months (less than or equal to 92 days) after the MRI has been obtained. Subjects should be exited if the EP visit cannot be done within 3 months after the MRI. In the case that the subject has not been exited and EP visit data has been obtained, this data cannot be included in the analysis since it might influence the validity of results.

Patients, who are not part of the Analysis Population, will not be included in the primary analysis of the primary objectives, but will be reported in the patient disposition table (number of patients per center). A secondary analysis might be performed including patients who were excluded of the analysis cohort. Safety will be reported on the All Enrolled Population and the primary objectives will be reported on the Analysis Population.

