**Table 1: Definition of Analysis Sets**

Cohort	Definition
All Enrolled	All patients that signed informed consent (i.e. informed consent date not blank)
Analysis	Enrolled Patients who have no inclusion or exclusion criteria violation regarding the most important criteria (i.e., inclusion criteria 1 and 2 and exclusion criterion 3) and who have less than three months between MRI and EP visit
Safety	All patients that signed informed consent

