## 7.2. General Methodology

Data summaries for categorical data will be summarized as count, e.g., number of patients, and/or number of events, and a percentage relative to the total number of patients/events. The denominator will be explicitly identified when not clear from the context. Continuous variables will be represented by mean and standard deviation, except when the distribution of the variable is highly skewed in which case median and quartiles will be reported.

P-values for hypothesis testing will be evaluated based on two-sided testing using significance level of 0.05 except for the non-inferiority testing (secondary objective 1) which is evaluated using one sided testing and a significance level of 0.025. Confidence intervals will be reported as two-sided 95% confidence intervals.

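### Percentages of patients with system-related or EP-procedure-related adverse events are taken over all consented patients, so they are diluted if anyone exits before the EP procedure

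*SAP*

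**What the plan says.** **Denominator.** SAP Table 1 defines the Safety set as "All patients that signed informed consent". SAP Table 2 assigns the adverse event and device deficiency summaries to that set. SAP 7.1.3 says "Safety will be reported on the All Enrolled Population", as does protocol H.1, and 7.10 repeats it: "Adverse events and device deficiencies will be summarized for the" All Enrolled cohort. Enrollment is at consent: "A subject is enrolled in the study when he/she signs and dates the Patient Informed Consent" (SAP 7.1.1).

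**Statistic.** SAP 7.10 plans tables with the "number and percentage of patients with one or more events", broken down among other things by relatedness to procedure and to system. SAP 7.2 expresses categorical data as a count and/or "a percentage relative to the total number of patients/events", and adds that "The denominator will be explicitly identified when not clear from the context". No set of patients who underwent the EP procedure is defined.

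**Exits before EP.** Protocol E.2.2 requires consent before any study activity. Under F.2.1.1, a patient with LBBB, QRS above 150 ms and no scar "should be exited from the study (if MRI done solely for the study"; the footnote to protocol Table 2 places that exit before the EP visit. Under F.3, a patient whose EP visit does not take place within 3 months of the MRI is also exited.

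**The concern.** Protocol F.6.1 ties system-related events to the pacing system, the leads, the introduction tools and the LV catheter. F.2.2 brings this equipment into use at the EP visit, and protocol Table 2 collects device deficiencies only there. A patient exited earlier can add to the denominator of a system-related percentage but never to its numerator.

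What is at stake is the risk per exposed patient. Protocol J.1 and J.2 say that there is no immediate direct benefit and that risk is believed to be somewhat higher than at a standard implant. Appendix L.2 foresees comparing observed events with earlier data to detect unexpected ones, and incidence is part of the USADE definition in F.6.1. Both uses need a rate among patients who were exposed.

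**Working it through.** **Inputs.** The documents state no adverse event rate, no rate of exit before EP and no fixed number of consented patients, so there is no figure of the plan to reproduce. Let C be the number consented (the denominator under SAP 7.1.3, 7.2 and 7.10), E the number in whom the EP procedure is started, and x the number of patients with at least one system-related event, all of whom lie within E.

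**Formula.**

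- Reported percentage = x / C
- Percentage among exposed patients = x / E
- Reported / exposed = E / C = 1 − (share of consented patients who exit before EP)

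The ratio is 1 if nobody exits early and below 1 otherwise. The direction needs no assumption; the size does.

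**Which number is 40?** SAP 7.1.1 and protocol C.8 describe enrolling up to 40 subjects who have completed the EP procedure, which points to E = 40 with early exits on top. The shell of SAP Table 4 heads the total column with N = 40, and 7.6 says that the table covers all enrolled patients as well as the analysis cohort, which points to C = 40. Both are shown, with k = 0 to 10 exits before EP (assumed) and x = 3 (illustrative).

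*E = 40, C = 40 + k: the percentage among exposed patients is 3/40 = 7.5% throughout.*

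| k | C | E/C | Reported, 3/C |
|---|---|---|---|
| 0 | 40 | 1.00 | 7.5% |
| 2 | 42 | 0.95 | 7.1% |
| 6 | 46 | 0.87 | 6.5% |
| 10 | 50 | 0.80 | 6.0% |

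*C = 40, E = 40 − k: the reported percentage is 3/40 = 7.5% throughout.*

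| k | E | E/C | Among exposed, 3/E |
|---|---|---|---|
| 0 | 40 | 1.00 | 7.5% |
| 2 | 38 | 0.95 | 7.9% |
| 6 | 34 | 0.85 | 8.8% |
| 10 | 30 | 0.75 | 10.0% |

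The largest gap in these ranges is 7.5 − 6.0 = 1.5 percentage points in the first case and 10.0 − 7.5 = 2.5 points in the second. In relative terms, the reported figure is up to 20% or 25% too low.

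**Can a reader recover the rate from other tables?** SAP 7.10 also reports counts, so E is all that is needed. SAP 7.1.1 promises a disposition flow chart, whose content cannot be seen here, and lists a table by visit or procedure only among those to be considered. SAP Table 2 assigns the attrition summary to the Analysis set. That set leaves out patients with key eligibility violations or a late EP visit even if they had the procedure (SAP 7.1.3), so its size is not E.

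**The case against.** The strongest reply is that All Enrolled was fixed in advance in both documents and suits adverse events collected from consent onwards. That stands for all-cause events and deaths. It does not stand for events that only exposed patients can have.

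Several further limits also stand, and each rules out a stronger reading:

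- *The rate will be understated.* A reader might infer this as a certainty, but exits could be zero. The scar route needs LBBB, QRS above 150 ms, no scar and an MRI done only for the study; the Table 2 footnote adds ischemic etiology. Under F.2.1.1, with a standard-of-care MRI the patient is not included at all, and F.2.1 allows baseline and EP on the same day.
- *The powered sample of 34 is the number exposed.* Protocol C.7 raises 34 to 40 for data collection problems during the EP procedure. Those patients are exposed, so 34 is not evidence of 6 earlier exits.
- *All procedure-related events belong to the EP visit.* F.6.1 covers any procedure related to the study procedure or protocol, which can include a study-only MRI, and it has a timing category that begins at consent. The argument is secure for system-related events and, within procedure-related events, for those due to the EP procedure.
- *Device deficiency percentages are diluted.* SAP 7.10 says only that deficiencies will be summarized and expressly plans no percentage of patients.
- *Upper confidence limits are understated, or the main safety result is biased.* Section 7.10 specifies no interval for adverse event percentages, and neither document has a safety objective or endpoint.

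The SAP also refers to a separate Safety Plan, which is not available here. Whether it defines a denominator of exposed patients cannot be checked.

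**Conclusion.** The concern holds for percentages of patients with system-related adverse events, USADEs and adverse events due to the EP procedure. The stated denominator includes patients who, by the protocol's own exit rules, may never reach the procedure. The percentage is too low by the factor E/C whenever at least one consented patient exits before EP, and unaffected otherwise. For 3 affected patients and an assumed 0 to 10 exits, the shortfall is 0 to 1.5 percentage points if 40 patients reach EP, and 0 to 2.5 points if 40 consent. The documents do not say where in these ranges the study will fall.

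The point does not extend to all-cause adverse events or deaths, for which All Enrolled is appropriate, and it touches none of the efficacy analyses.

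**What to change.** In SAP Tables 1 and 2, add a set of patients in whom the EP study procedure was started, whether or not it was completed. In 7.10, make it the denominator for system-related adverse events, USADEs and adverse events related to the EP procedure, and for device deficiencies if a percentage of patients is given.

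Keep All Enrolled for all-cause adverse events, deaths and listings, and for events related to a study-only MRI or other activity before EP, so that every numerator stays within its denominator. State the denominator in each table. The Analysis set should not be used instead.

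The cost is one added denominator and slightly less favourable percentages if anyone exits early. No new data are needed and no objective changes. Because protocol H.1 names All Enrolled for safety, record the addition in SAP 7.12.

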### **7.11. Health Outcomes Analyses**

No health outcomes analysis is planned for the SYNSEQ study.

### **7.12. Changes to Planned Analysis**

This Statistical Analysis Plan does not deviate from the planned statistical analysis in the CIP. The analysis cohort has been described in the CIP as follows: "The Analysis Population is defined as patients, who are enrolled, have no inclusion or exclusion criteria violation regarding the most important criteria, i.e., inclusion criteria 1 and 2 and exclusion criterion 3, and for whom the EP procedure could be completed successfully." This definition has been clarified in the SAP to the following definition: "The Analysis Population is defined as patients who are enrolled, have no inclusion or exclusion criteria violation regarding the most important criteria, i.e., inclusion criteria 1 and 2 and exclusion criterion 3, and have less than 3 months between MRI and EP visit."

Any change to the data analysis methods described in the Clinical Investigational Plan will require an amendment only if it changes an objective of the Clinical Investigational Plan. Any other change to the data analysis methods described in the Clinical Investigational Plan and this Statistical Analysis Plan, and the justification for making the change, will be described in the clinical study report. Additional exploratory analyses of the data will be conducted as deemed appropriate.

---

**8.** [REDACTED]

[REDACTED]

[REDACTED]

[REDACTED]

[REDACTED]

[REDACTED]	[REDACTED]	[REDACTED]
[REDACTED]	[REDACTED]	[REDACTED]
[REDACTED]	[REDACTED]	[REDACTED]
[REDACTED]	[REDACTED]	[REDACTED]
[REDACTED]	[REDACTED]	[REDACTED]
[REDACTED]	[REDACTED]	[REDACTED]
[REDACTED]	[REDACTED]	[REDACTED]

